Laboratory Sessions. Consistent with previous work ([name], et al., 2014; Lewis, et al., 2013), participants will be asked to fast for at least 4 hours prior to their scheduled session and abstain from alcohol consumption 24 hours before each of the two laboratory sessions. Use of non-steroidal anti-inflammatory drugs (NSAIDs) in the 12 hours prior to testing will also be restricted. Normal morning medications will be permitted, but OTC medications (including allergy medications and analgesics) will not be allowed. **A urine- based drug screen for tetrahydrocannabinol, cocaine, benzodiazepines, morphine, and methamphetamine (Innovacon, Inc., San Diego, CA) will be performed. Participants testing positive for any substance will be discontinued. A baseline breath alcohol concentration (BrAC) measure will be taken, which must be negative.** Women will complete a brief questionnaire regarding their menstrual cycle, including: 1) if they are currently menstruating or post-menopausal; 2) typical time between menstruation; 3) days elapsed since last menses; 4) typical menses length; and 5) use of any hormonal preparations (e.g., birth control). **Women of child bearing potential will be given a pregnancy test; positive tests will result in exclusion from the study with a recommendation to contact her physician.** Women who are currently breastfeeding will also be discontinued. All testing will be conducted in private rooms within the Center for Pain Research and Behavioral Health. Participants will be provided with a light breakfast one hour before alcohol administration (~200 kcal). Following breakfast, participants will repeat affective measures (BDI-II/STAI) as well as an Irritability Questionnaire (IRQ; Craig et al., 2008). Lunch will be provided following testing, as well as another light meal as needed. At the conclusion of their final laboratory session, individuals in the TMD group will also be asked whether and how frequently (never, sometimes, frequently, always) they have used alcohol to help control their TMD pain (Riley and King, 2009). For laboratory sessions, the PI or a research assistant will schedule a ride with Uber or Lyft to drive participants home after the completion of the session. Research assistants will use the GPS features of the rideshare app to ensure that participants make it home safely. If the rideshare app indicates that the participant was dropped off somewhere other than the vicinity of their home, the attending researcher will call the number left by the participant and speak with the participant. If the participant does not answer the phone, the researcher will contact the IRB to report the protocol deviation. Participants will be paid \$50 for completing each of the two laboratory sessions. Laboratory sessions will be separated by at least 48 hours.

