
Alcohol Administration. Alcohol administration procedures are consistent with our previous work and NIAAA guidelines for the safe and ethical administration of alcohol in

experimental settings (Brown et al., 2014). Participants will complete two laboratory sessions in which they will be administered one of two beverages: placebo (0.00 g/dL target BrAC) or active alcohol (0.08 g/dL target BrAC). Session order will be counterbalanced across participants. For laboratory sessions in which a participant will be given the active dose, the quantity of medical/United States Pharmacopeia grade alcohol (100% or 95% ethanol) needed to achieve 0.08 g/dL (i.e., approximately 3-4 standard drinks) will be calculated using a modification of the Widmark formula. This formula utilizes age and weight measures for men and height and weight measures for women (Watson, et al., 1981; Widmark, 1932). For example, a 30-year old man who is 183 cm tall and weighs 75 kg would receive 55.3 ml of absolute ethanol, or ~.58 g/kg. In order to maintain the study's double blind, a researcher not involved in QST will be responsible for calculating alcohol doses and mixing drinks, and the dose calculation and mixing procedure confirmed by a second research assistant. Pre-calculated dose lookup tables indexing height and weight for women and age and weight for men will be used to avoid dosing errors. Alcohol will be mixed with cold sugar-free lemon-lime soda in a 1:3 ratio and split into two servings ([name], et al., 2014; Gilbertson, et al., 2009; Harrison et al., 2007). Placebo beverages will consist of only soda. Participants will consume both servings within 5 minutes. **Both active and placebo drinks will be misted with alcohol to enhance placebo effectiveness. A small amount of alcohol will be placed on the rim of the glass and floated on the surface of the beverage to further mask the study condition.** Participants will rinse their mouths thoroughly with water once their beverage has been consumed. No suggestion regarding the potential pain-relieving effects of alcohol will be provided before or after beverage administration to avoid influencing expectations. All study staff over the age of 21 designated as "Interacts or intervenes directly with study subjects" on the myIRB smart form will be trained by the PI how to use the lookup tables and mix beverages and may serve in this capacity depending on availability for a given laboratory session.

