Psychological Discomforts and Risks. Some aspects of the questionnaires utilized in this proposal may make study participants uncomfortable, especially those dealing with affect or medical history. To ameliorate this possibility, participants will be informed they can withdraw from the study at any time or skip individual questions that may be upsetting to them.

Acute Alcohol Intake. Alcohol intake may result in dizziness, nausea, and vomiting should a participant tolerate the active dose of alcohol poorly. The risk of these as well as more serious consequences may increase if a participant uses medications that contraindicate the use of alcohol (e.g. benzodiazepines/opioid analgesics). Should a participant experience any of these symptoms, they will be allowed to rest until symptoms subside and will be allowed to withdrawal from the study if desired. We have attempted to minimize this risk by recruiting only those who are regular moderate drinkers and excluding those regularly taking prescription medications that contraindicate the use of alcohol. Ss will be rescheduled if they report having taken prescription or over-the-counter medications that contraindicate alcohol use on the day of testing.

Pregnancy: Alcohol intake is an unacceptable risk in pregnancy. Therefore, anyone of childbearing potential will be tested for pregnancy on the morning of the laboratory session. Positive pregnancy tests will result in exclusion from study and lab staff will assist in making a referral as appropriate. Finally, any documents associated with a participant testing positive for pregnancy will be destroyed without reference to a specific cause.

Breath Analyzer Testing: Breath analyzer testing may result in dizziness or lightheadedness for some individuals. However, the PI has administered many of these tests and never observed a significant negative consequence. Staff will be trained to recognize discomfort resulting from breath analyzer testing and will assist participants in

ameliorating symptoms should they occur (eg., discontinue testing, place head between knees, etc.).

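### The rule to destroy records after a positive pregnancy test is not limited to positives before dosing, so a woman given alcohol at session 1 could have that record destroyed without first being told what she drank

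*Combined protocol and SAP*

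**What the plan says.** Section 7, Pregnancy, takes a firm position: "Alcohol intake is an unacceptable risk in pregnancy". It therefore requires that "anyone of childbearing potential will be tested for pregnancy on the morning of the laboratory session". After a positive test the participant is excluded and "lab staff will assist in making a referral as appropriate". The paragraph closes with the destruction rule: "any documents associated with a participant testing positive for pregnancy will be destroyed without reference to a specific cause".

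Section 6 supplies the design around that rule. The pregnancy test appears under Laboratory Sessions as part of the session procedure, with advice to the woman to contact her physician. On spacing, "Laboratory sessions will be separated by at least 48 hours"; no maximum is given. Under Alcohol Administration, each participant receives placebo at one session and alcohol (target 0.08 g/dL, roughly 3 to 4 standard drinks) at the other, and "Session order will be counterbalanced across participants". To protect the blind, "a researcher not involved in QST will be responsible for calculating alcohol doses and mixing drinks", and a second assistant confirms the calculation and mixing.

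**The concern.** The destruction sentence reads as though a positive test always comes before anything has been given. In a two-session crossover that is true only at session 1. A positive at session 2 comes after a completed session, which for about half of participants was the alcohol session. The rule makes no distinction between the two situations.

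At stake is what a newly pregnant participant and her physician can be told. She knows when she attended and may have a view on what she drank, since the protocol asks her what she believes she received. But the placebo is deliberately masked, so her belief does not settle whether she had alcohol or how much. The protocol itself treats this exposure as unacceptable, yet its text has no step for passing on the answer and none for keeping the record that would support it.

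**Working it through.** The plan gives no figure on this point, so the check is mainly a reading of the text.

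**Can the situation arise?**

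1. Each test precedes that day's drink, so a positive at session 1 involves no study exposure. Destruction is harmless there.
2. A positive at session 2 follows the session 1 drink. This assumes that the test is repeated at session 2. Section 7 refers to the session in the singular, but Section 6 places the test in the general session procedure. Because about half of participants receive alcohol at session 2, testing at both is the natural reading.
3. The gap is at least 48 hours with no upper limit, so a pregnancy too early to detect at session 1 could become detectable by session 2.
4. The destruction sentence has no limit by timing, by type of document or by prior dosing. No other section exempts this participant.

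**Is there a step that protects her?**

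- Section 6 gives advice to see a physician and Section 7 a referral. Neither mentions the earlier beverage.
- The confidentiality text in Section 7 describes secure storage of paper and digital data. It sets no retention rule for this case.
- The Data and Safety Monitoring Plan provides quarterly meetings and defers to NIH and university policy. It does not require records to be kept until a meeting.

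**How many women could be in this position?** Inputs: 60 recruits and N = 50 (Power Analysis), about 2/3 women (Participants), about half with alcohol first (counterbalancing).

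- At 60: 60 × 2/3 = 40 women; 40 × 1/2 = 20 with alcohol first.
- At 50: 50 × 2/3 = 33.3 women; 33.3 × 1/2 = 16.7, about 17 with alcohol first.

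These are ceilings, because not every woman is of childbearing potential.

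**How often would it happen?** The documents give no pregnancy rate. Purely as an illustration, assume that 0.1% to 1% have a pregnancy undetected at session 1, and that 25% to 100% of those turn positive by session 2.

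- Expected alcohol-first cases, low: 17 × 0.001 × 0.25 = 0.004.
- Expected alcohol-first cases, high: 20 × 0.01 × 1 = 0.20.
- Chance of at least one, low: 1 − (1 − 0.00025)^17 = 0.4%.
- Chance of at least one, high: 1 − 0.99^20 = 18%.

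The upper figure takes the highest value of every input together. A conception after session 1 would also trigger destruction, but without exposure from session 1, and is not counted.

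**Effect on the analysis.** A woman excluded before her second drink contributes no alcohol-versus-placebo contrast, so neither the aims nor the power depends on her records.

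**The case against.** The strongest reply is that the answer would rarely be lost. There are only two beverages, one per session, so whoever is to prepare session 2 can infer session 1 from what is due. Counterbalancing needs an order assignment of some kind. The dose comes from lookup tables on height and weight for women, so it can be recalculated. Referral is described before the destruction step, which leaves time to tell her. The documents do not say where the beverage is recorded or whether the rule reaches digital files, and the consent pages are not in the text reviewed. All of this stands. A reader might infer from the destruction sentence that her exposure becomes unknowable; the documents do not support that. What remains is that no one is told to inform her, and that her measured breath alcohol readings, unlike the dose, cannot be recalculated.

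A second reply is that the event is rare and any incidence figure is assumed. That also stands. A reader might take the 18% above as a forecast, but it has no basis in the documents and the conclusion does not use it.

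A third concerns IRB reporting. A reader might infer an omission because the protocol names IRB reports elsewhere: for pain continuing at 24 hours and, for a participant who cannot be reached after the ride home, "the researcher will contact the IRB to report the protocol deviation". Those cover an adverse event and a deviation. A positive test that leads to exclusion is the protocol working as written, so the comparison does not show that a report was left out.

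Finally, participants are all current drinkers, so the study dose may not be the only exposure to discuss. True, but that does not tell her what the study gave her.

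**Conclusion.** The point holds as a minor participant-safety correction. The rule as written would allow participant-level session 1 records to be destroyed after a woman has been given alcohol, with no instruction to tell her first which beverage she had. This rests on the unrestricted wording and on the reading that testing is repeated at session 2.

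It does not extend to a finding that the information would be permanently lost, nor to any estimate of frequency beyond a ceiling of about 17 to 20 women with alcohol first, of whom only a small fraction could be affected. Confidence is high in the wording gap and lower in its consequence, since a study-level order assignment, digital files or consent wording may cover part of it.

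**What to change.** Limit the last sentence of the Pregnancy paragraph to participants who test positive before receiving any study beverage. For a positive test after a completed session, add:

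- At referral, an unblinded staff member tells the participant her session 1 beverage, dose and date.
- The coded session 1 dosing and session records are kept under the confidentiality safeguards already in Section 7.
- She is counted as a post-dosing withdrawal, with no reason shown in the study data.
- Any IRB report is made under the NIH and university policy to which the Data and Safety Monitoring Plan already refers. The amendment should acknowledge that such a report would state the cause to the IRB, even though the study data do not.

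The cost is a short amendment, one disclosure step in a rare case and, if the consent form describes the destruction rule, matching wording there. The downside is that a few sensitive coded records are kept that would otherwise be destroyed. Her exclusion precedes session 2, so telling her breaks no blind that is still needed.
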